Key exclusion criteria	
Patients with a history of seizures, significant liver dysfunction, renal dysfunction, significant upper or lower limb arthritis or any other disorder including cognitive dysfunction which would affect the ability to accurately complete questionnaires and give full informed consent.
 
Patients with clinically significant upper limb ataxia or upper limb proprioceptive sensory loss, which in the opinion of the Clinician affect upper limb functional assessment. Patients concomitantly using medicinal products that are inhibitors of Organic Cation Transporter 2 (OCT2).
 
Patients on concurrent treatment with other medicinal products containing fampridine (4-aminopyridine). Pregnant or breast-feeding patients.

Number of subjects	80
Test product, dose and mode of administration	
Oral PR-Fampridine 10mg b.d
 
Oral Placebo one tablet b.d.

Duration of treatment	Two 8 week treatment periods
Statistical methods	Participants will be classified as to whether they are “responders” or “non-responders” by the 9-HPT and the T25FW according to defined criteria. Change in the MSWS-12, the MSIS-29 (physical) and the DASH and AMSQ in responders and non-responders will be examined by the Wilcoxin Signed Rank test to assess the significance of the mean differences between groups.
Sample size	80

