9.1 PRIMARY OBJECTIVE

The primary objective is to assess the effect of treatment with oral PR-fampridine in patients with secondary progressive MS (SPMS) or primary progressive MS (PPMS) with upper limb dysfunction (as defined by a 9-HPT time of between 15-90 seconds) and Kurtzke EDSS¹⁴ scores in the range 4.0-7.0 on Upper limb function assessed by the nine-hole peg test (9-HPT) and the Jebson Taylor Hand Function Test (JTT). Scores of the MSIS-29 (physical), MSWS-12 and the Disabilities of the Arm, Shoulder and Hand Score (DASH)¹⁰ and the Arm Function in Multiple Sclerosis Questionnaire (AMSQ)¹⁹.

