9.2 SECONDARY OBJECTIVE

Secondary objectives are:

To assess the effect of treatment with fampridine on walking mobility assessed by the Timed 25 foot Walk (T25FW) and the Multiple Sclerosis Walking Scale (MSWS-12)^{6,7}

To determine whether response or non-response to fampridine by the T25FW can be easily determined using self reported changes in the MSWS-12 alone within 4 weeks in the course of active therapy

To determine whether response or non-response to fampridine by the 9HPT or JTT can be easily determined using self reported changes in the DASH and AMSQ alone within 4 weeks on the course of active therapy

To determine whether any relation exists between improvement / lack of improvement on the T25FW and improvement/ lack of improvement on the 9-HPT or JTT.

To examine the safety of fampridine in this patient population

To assess the impact of fampridine on health related quality of life in patients with multiple sclerosis (HRQOL) as measured by the SF-36 questionnaire.

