13.5 EFFICACY ANALYSIS

Primary efficacy endpoint:

An upper limb responder to fampridine will be defined as a patient with both of the two "on treatment" 9-HPT assessments (assessments 4 & 5 or 7 & 8) improving 20% from the average of the baseline assessments (1, 2 & 3).

Secondary efficacy endpoints:

- a) A secondary measure of upper limb responsiveness will be defined as a 20% improvement in from baseline in the average time taken to complete all seven tasks on the JTT “on treatment” (assessments 4 & 5 or 7 & 8) compared with baseline assessments (assessments 1,2 & 3).
- b) A mobility responder to dalfampridine will be defined as a patient with both of the two “on treatment” T25FW assessments (assessments 4 & 5 or 7 & 8) being better than the maximum of any of the four “off treatment” assessments (assessments 1, 2, 3, & 9). Otherwise the patient will be deemed a non-responder.
- c) The responders to the 9-HPT and/or JTT will be compared to the non-responders in relation to their changes in the DASH and AMSQ on treatment and off treatment at the baseline assessment. The change in the DASH and AMSQ in responders at Assessment 5 or 8 (week 10 or 20) will be compared to non-responders at that time-point.

Upper limb response will be examined at the end of treatment phase 1 and repeated at the end of the trial by comparing patients receiving active drug with those receiving placebo to assess any placebo effect and allow assessment of any residual beneficial effect on those who receive fampridine in treatment phase 1 and then switch to placebo in treatment phase 2. Response will again be considered as a 20% improvement in the 9HPT in the active treatment group compared with placebo and a 20% improvement from baseline in the time taken to complete all seven tasks in the JTT. See earlier comment

- d) The responders to the T25FW will be compared to the non-responders in relation to their changes in the MSWS-12 on treatment and off treatment at the baseline assessment. The change in the MSWS-12 in responders at Assessment 5 or 8 (week 10 or 20) will be compared to non-responders at that time-point.

The patients’ scores on the MSIS-29 (physical) and SF-36 will be examined in relation to the objective changes (responder/non-responder) in the 9-HPT, JTT and the T25FW.

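### SF-36, MSIS-29, MSWS-12 and T25FW have no named fampridine v placebo analysis, and the responder v non-responder contrast that is named cannot answer the drug-effect objectives

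*Combined protocol and SAP*

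**What the plan says.** Two secondary objectives in 9.2 are drug-effect questions: "To assess the impact of fampridine on health related quality of life in patients with multiple sclerosis (HRQOL) as measured by the SF-36 questionnaire", and "To assess the effect of treatment with fampridine on walking mobility assessed by the Timed 25 foot Walk (T25FW") together with MSWS-12. MSIS-29 (physical) is in neither. It is listed in the primary objective (9.1), in a fragment that begins "Scores of the MSIS-29 (physical), MSWS-12 and the Disabilities of the Arm, Shoulder and Hand Score (DASH") and states no analysis.

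Section 13.5, repeated in 9.4 and 10.3.2, gives the analyses that name these measures. For SF-36 and MSIS-29, the patients' "scores on the MSIS-29 (physical) and SF-36 will be examined in relation to the objective changes (responder/non-responder") in 9-HPT, JTT and T25FW. For MSWS-12, "The responders to the T25FW will be compared to the non-responders in relation to their changes in the MSWS-12 on treatment and off treatment", where off treatment refers to the baseline assessment and not to the placebo phase. It adds that "The change in the MSWS-12 in responders at Assessment 5 or 8 (week 10 or 20) will be compared to non-responders". T25FW appears as the rule that defines a mobility responder. The synopsis says that change in MSWS-12 and MSIS-29 (among others) "in responders and non-responders will be examined by the Wilcoxin Signed Rank test"; it does not name SF-36 there.

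Section 13.1 adds one general sentence: a Wilcoxon signed-rank test of paired on-treatment outcome measures within each individual. Section 13.2 treats observations as paired within individuals.

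A different objective in 9.2 does concern responders: whether T25FW response "can be easily determined using self reported changes in the MSWS-12 alone within 4 weeks in the course of active therapy". A parallel objective covers DASH and AMSQ.

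**The concern.** Whether a patient is a responder is known only after treatment and is decided by an outcome. Randomisation therefore does not protect a comparison of responders with non-responders. The timed tests and the questionnaires are taken at the same visits, so a patient in a good spell tends to do better on both. Responders can then report better quality of life or walking even if the drug does nothing. The opposite error is also possible: a benefit shared by everyone shifts both subsets equally and does not show in the contrast.

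At stake is the reading of the secondary results. A report of better SF-36 or MSWS-12 in responders could be taken as a drug effect, while the randomised placebo-phase scores enter no analysis that names them. The test of the primary endpoint is not affected by this point.

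**Working it through.** **Step 1: objectives against named analyses.**

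| Measure | Objective | Analysis that names it | Named fampridine v placebo analysis |
|---|---|---|---|
| SF-36 | 9.2, drug effect | By responder status (13.5, 9.4, 10.3.2) | None |
| MSWS-12 | 9.2, drug effect; also listed in 9.1 | T25FW responders v non-responders (same sections, synopsis) | None |
| T25FW | 9.2, drug effect | Defines the mobility responder | None |
| MSIS-29 (physical) | Listed in 9.1 | By responder status (same sections, synopsis) | None |
| 9-HPT, JTT | 9.1 | Responder rules | Yes: end of phase 1 and end of trial (13.5) |

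Figure 2 schedules all of these at Assessments 4, 5, 7 and 8, so each patient who completes both phases supplies two fampridine-phase and two placebo-phase values. The plan gives no power or precision figure for these outcomes, so there is none to reproduce.

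**Step 2: chance responders on an inert drug.** Take the T25FW rule as both on-treatment walks beating all four off-treatment walks. If the six results are exchangeable, this happens by chance with probability 1/C(6,2) = 1/15 = 6.7%, or 80/15 = about 5 of 80 patients. If half of the fluctuation variance is common to a treatment phase (assumed), simulation gives about 14%.

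**Step 3: the resulting gap.** Let r be the correlation between the timed-test change and the questionnaire change, and treat responders as the top fraction p of a normal change score (a simplification). The gap, in SD of questionnaire change, is r × φ(z)/[p(1 − p)].

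- p = 1/15: φ(1.501)/(0.0667 × 0.9333) = 0.1293/0.0622 = 2.08
- p = 0.14: φ(1.080)/(0.14 × 0.86) = 0.2226/0.1204 = 1.85

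A two-sided 5% Mann-Whitney test was simulated for 72 patients (80 less an assumed 10% loss):

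| p | r | Gap (SD) | Test positive |
|---|---|---|---|
| 6.7% | 0 | 0 | 4-5% |
| 6.7% | 0.2 | 0.42 | 12-14% |
| 6.7% | 0.4 | 0.83 | 38-39% |
| 14% | 0 | 0 | 5% |
| 14% | 0.2 | 0.37 | 16-17% |
| 14% | 0.4 | 0.74 | 57% |

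The ranges cover separate runs, including runs with the number of responders fixed or left random.

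**Step 4: check with the actual visit structure.** An inert drug was simulated through the nine assessments with 80 patients. Under the T25FW rule the contrast favoured responders significantly in 11-24% of trials at a within-visit correlation of 0.3, and in 25-58% at 0.5. Under the 9-HPT rule (assumed visit-to-visit CV 15-20%, half the fluctuation shared within a phase) the figures were 22-28% and 48-65%. The within-patient active v placebo signed-rank test rejected in 4-6% of trials throughout.

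**Step 5: uniform benefit.** Write each patient's change as δ + e. The responder contrast is (δ + E[e | responder]) − (δ + E[e | non-responder]), and δ cancels. Whatever gap remains is the selection effect of Step 3.

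**Step 6: precision of the paired contrast.** The smallest difference detectable with 80% power is (1.960 + 0.842)/√(0.955n), where 0.955 is the efficiency of the signed-rank test. This gives 0.32 SD of the paired difference for n = 80 and 0.36 SD for n = 64. As an illustration, section 8.2 cites a 7-point MSWS-12 gain in about one third of patients, a mean of 7/3 = 2.3 points. With an assumed paired-difference SD of 10 to 20 points, power with 80 patients falls from 53% to 17%.

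**The case against.** The strongest reply is that 13.1 already supplies the missing analysis. In a two-period crossover, a signed-rank test on values paired within the individual is naturally read as one phase against the other, and 13.2 supports that. This stands to the extent that a reader who infers that these scores are analysed only by responder status, or that the plan excludes a randomised comparison, goes too far. But 13.1 names no questionnaire, assessment or comparator. In the responder definitions, on treatment refers to one pair of visits, either 4 and 5 or 7 and 8, which are the visits used to label a fampridine responder. An analyst who follows the more specific text in 13.5 would produce only the responder contrast.

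Second, the responder contrast is the right tool for whether MSWS-12 change identifies T25FW response, and DASH or AMSQ change identifies upper limb response. That stands. A reader might infer that the contrast should be dropped or wholly demoted, and the objectives in 9.2 do not support that. Nor do the documents say that it will be reported as a drug effect.

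Third, the false-positive rates depend on a correlation that the documents do not give; at zero correlation there is no inflation. That stands too, although the MSWS-12 objective itself expects the two measures to move together. A reader might also apply the 30% response figure in 13.2 to an inert drug, which with a correlation of 0.4 would raise the rate to about 73%. That figure is the improvement anticipated on treatment, not a chance rate. Similarly, one might infer that a uniform benefit makes the responder difference zero. That is true only at zero correlation; in general the benefit just adds nothing.

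**Conclusion.** The concern holds in this form: 9.2 poses drug-effect questions for SF-36, T25FW and MSWS-12, and 9.1 lists MSIS-29 (physical), yet no fampridine v placebo analysis is named for any of the four. The contrast that is named for the questionnaires does not estimate a drug effect. Its false-positive rate with an inert drug is about 14-57%, with a gap of about 0.37-0.83 SD, if the correlation is 0.2-0.4, chance responders are 7-14% and 72 patients are analysed. The correlation, the share of fluctuation within a phase and the patient loss are assumptions. The structural point, that the split is post-treatment and a uniform effect cancels, needs none of them. These are secondary or listed measures, so the change should be made, but it does not bear on the primary endpoint test.

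**What to change.** In 13.5, 9.4 and 10.3.2, state that the treatment-effect analysis of SF-36, MSIS-29 (physical), MSWS-12 and T25FW time is the within-patient fampridine-phase minus placebo-phase difference, using Assessments 4 and 5 against 7 and 8. Adjust it for period, because 10.3 allows for training effects, and give a confidence interval. Report all four as secondary: 13.7 applies 0.05 to every analysis, so four more tests should not be read as four confirmatory claims. Cross-refer 13.1 to this definition so that its pairing is explicit.

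Keep the responder v non-responder analysis for the objectives on whether MSWS-12, DASH or AMSQ change identifies response. State that it will not be reported as a drug effect on SF-36, MSIS-29 or MSWS-12. Print the same table for the placebo phase, with the responder rule applied to the placebo visits, as the no-drug reference.

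The cost is SAP wording and a few extra tables, with no new visits or data. Power for these outcomes may be modest, which is a further reason to present confidence intervals rather than tests alone.

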9.4 PRIMARY AND SECONDARY/ EXPLORATORY ENDPOINTS/OUTCOME MEASURES

Primary endpoint:

The primary end point will be identifying an upper limb responder to fampridine defined as a patient with both of the two “on treatment” 9-HPT assessments (assessments 4 & 5 or 7 & 8) improving 20% from the average of the baseline assessments (1, 2 & 3).

Secondary endpoints:

A secondary measure of upper limb responsiveness will be defined as a 20% improvement in from baseline in the average time taken to complete all seven tasks on the JTT “on treatment” (assessments 4 & 5 or 7 & 8) compared with baseline assessments (assessments 1,2 & 3).

A mobility responder to Fampridine will be defined as a patient with both of the two “on treatment” T25FW assessments (assessments 4 & 5 or 7 & 8) being better than the maximum of any of the four “off treatment” assessments (assessments 1, 2, 3, & 9). Otherwise the patient will be deemed a non-responder.

The responders to the 9-HPT and/or JTT will be compared to the non-responders in relation to their changes in the DASH and AMSQ on treatment and off treatment at the baseline assessment. The change in the DASH and AMSQ in responders at Assessment 5 or 8 (week 10 or 20) will be compared to non-responders at that time-point.

Upper limb response will be examined at the end of treatment phase 1 and repeated at the end of the trial by comparing patients receiving active drug with those receiving placebo to assess any placebo effect and allow assessment of any residual beneficial effect on those who receive fampridine in treatment phase 1 and then switch to placebo in treatment phase 2. Response will again be considered as a 20% improvement in the 9HPT in the active treatment group compared with placebo and a 20% improvement from baseline in the time taken to complete all seven tasks in the JTT. See earlier comment

The responders to the T25FW will be compared to the non-responders in relation to their changes in the MSWS-12 on treatment and off treatment at the baseline assessment. The change in the MSWS-12 in responders at Assessment 5 or 8 (week 10 or 20) will be compared to non-responders at that time-point.

The patients’ scores on the MSIS-29 (physical) and SF-36 will be examined in relation to the objective changes (responder/non-responder) in the 9-HPT, JTT and the T25FW.

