10.3 STUDY ASSESSMENTS AND PROCEDURES

Patients likely to fulfill the inclusion criteria and not meet any exclusion criteria will be provided with information on the study and invited to attend a subsequent screening visit. Only patients who have signed the informed consent form will participate in any study related procedures including blood testing and ECG.

At screening visit (Assessment 1) subjects will have a physical examination and an EDSS score rated. Blood samples will be taken for renal and liver function and a baseline ECG performed. Patients will complete a nine-hole peg test and a JTT. T25FW will be recorded and the patients invited to complete the MSIS-29, MSWS-12, DASH, AMSQ and SF-36 questionnaires. Patients with any abnormalities on ECG, blood tests will not be invited to a baseline visit and considered a screening failure.

Following screening visit subjects fulfilling the inclusion / exclusion criteria will have two baseline visits (Assessments 2 and 3) at the end of week one and end of week two. The 9-HPT, JTT and T25FW will be repeated to allow for training effects. Patients will be randomised to group A or group B and receive study medication or placebo at baseline visit based on their blinded randomisation (Assessment 3).

The first treatment period will be from the start of week 3 until the end of week 10. Patients will have an assessment at the end of week 6 (Assessment 4) and the end of week 10 (Assessment 5). At both assessments patients will have the 9-HPT, JTT, T25FW, MSIs-29, MSWS-12, DASH, AMSQ and SF-36 recorded. Weeks 11 and 12 will be a washout period (no drug/placebo). Assessment 6 will occur at the end of week 12 and will include recording of 9-HPT, JTT, T25FW, MSIs-29, MSWS-12, DASH, AMSQ and SF-36. Any adverse events will be recorded at each visit as will the use of concomitant medications.

The second treatment period will begin at the start of week thirteen with groups A and B switching study drug / placebo in a blinded manner. The second treatment period will continue for a further 8 weeks with two more assessments at week 16 (Assessment 7) and week 20 (Assessment 8). At both of these assessments subjects will complete the 9-HPT, JTT, T25FW, MSIs-29, MSWS-12, DASH, AMSQ and SF-36. At the end of week 20 and EDSS score will be recorded. Any adverse events will be recorded at each visit as will the use of concomitant medications.

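### The MSIS-29 (physical) and SF-36 are related to responder status as scores, with no baseline and no visit, unlike the other questionnaires and, for the MSIS-29, unlike the synopsis

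*Combined protocol and SAP*

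**What the plan says.** Section 13.5 treats the questionnaires in two ways.

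- **DASH and AMSQ (endpoint c):** "The change in the DASH and AMSQ in responders at Assessment 5 or 8 (week 10 or 20) will be compared to non-responders" at the same time-point.
- **MSWS-12 (endpoint d):** "The change in the MSWS-12 in responders at Assessment 5 or 8 (week 10 or 20) will be compared to non-responders" at the same time-point.
- **MSIS-29 (physical) and SF-36 (last paragraph):** "scores on the MSIS-29 (physical) and SF-36 will be examined in relation to the objective changes (responder/non-responder"). No change, baseline, visit or test is given. Sections 9.4 and 10.3.2 carry the same sentence; in 9.4 it reads "SF-36 will be examined in relation to the objective changes (responder/non-responder) in the 9-HPT, JTT and the T25FW".

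The synopsis, under statistical methods, differs: "Change in the MSWS-12, the MSIS-29 (physical) and the DASH and AMSQ in responders and non-responders will be examined". That covers the MSIS-29 (physical) but leaves out the SF-36.

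The SF-36 is the instrument named for the quality of life objective in 9.2: "To assess the impact of fampridine on health related quality of life in patients with multiple sclerosis (HRQOL) as measured by the SF-36 questionnaire".

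Both questionnaires are collected before treatment. At screening, "T25FW will be recorded and the patients invited to complete the MSIS-29, MSWS-12, DASH, AMSQ and SF-36 questionnaires", and the schedule of events (Figure 2) marks both again at Assessment 3, before the first dose.

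**The concern.** Responder status is decided by each patient's own 9-HPT, JTT or T25FW results on treatment. The two groups are therefore not randomised groups and may differ before any drug is taken. Entry allows EDSS 4.0 to 7.0 and a 9-HPT time of 15 to 90 seconds, so there is room for patients to differ widely in physical impact and quality of life at the start.

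If on-treatment scores are compared as they stand, such a difference passes straight into the result. If responders start milder, the SF-36 appears to track response although nobody changed. If they start worse, a real gain is masked. Even with equal baselines, stable variation between patients costs power.

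The open wording also lets the analyst choose between score and change, and choose the visit, after seeing the data.

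**Working it through.** **1. Text comparison**

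| Scale | Synopsis | 13.5 | Visit in 13.5 |
|---|---|---|---|
| DASH, AMSQ | change | change | Assessment 5 or 8 |
| MSWS-12 | change | change | Assessment 5 or 8 |
| MSIS-29 (physical) | change | scores | none |
| SF-36 | not listed | scores | none |

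For the MSIS-29 (physical) the document disagrees with itself. For the SF-36 the quantity is left open throughout. The plan gives no numerical figure for this analysis, so there is none to reproduce.

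**2. Inputs for an illustration**

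- From 13.2: 80 patients and about 30% responders, so 0.30 × 80 = 24 responders and 56 non-responders.
- From 13.7: significance level 0.05, taken here as two-sided.
- Assumed, not in the documents: on-treatment SD of 1; correlation ρ between baseline and on-treatment score of 0.6 to 0.8; a stable pre-treatment gap of 0.3 or 0.5 SD; where there is a true gain, 0.4 SD in responders.

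**3. No true change, raw scores**

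Standard error of the group difference = √(1/24 + 1/56) = 0.244 SD. The rejection rate is about 1 − Φ(1.96 − gap/0.244); the opposite tail is negligible.

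- Gap 0.3: 0.3/0.244 = 1.23, rejection about 23%.
- Gap 0.5: 0.5/0.244 = 2.05, rejection about 54%.

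A simulated rank-sum test (4,000 trials per setting) gives slightly lower values: about 20–22% and 49–51%.

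**4. No true change, change scores**

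A stable gap cancels when the baseline is subtracted, so the rejection rate stays at about 5% for any ρ.

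**5. True gain of 0.4 SD (simulated rank-sum test)**

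| Starting point | Raw score | Change, ρ = 0.6 to 0.8 |
|---|---|---|
| Equal baselines | about 34–35% | about 41–70% |
| Responders 0.3 SD worse | about 6–7% | about 41–71% |

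In the second row the raw difference shrinks to 0.4 − 0.3 = 0.1 SD.

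**6. Where change is noisier**

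With one baseline visit, the variance of change is 2(1 − ρ). It exceeds the raw variance of 1 when ρ is below 0.5. With the mean of two baseline visits, and the same ρ between every pair of visits, it is 1 + (1 + ρ)/2 − 2ρ = 1.5(1 − ρ), and the break-even falls to ρ = 1/3.

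**7. Baseline adjustment as the alternative**

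Regression on baseline (a single baseline here) removes ρ × gap and leaves (1 − ρ) × gap. With ρ = 0.7 and a stable gap of 0.5 SD, 0.15 SD remains, with residual SD √(1 − 0.49) = 0.714. Then 0.15/(0.714 × 0.244) = 0.86 and rejection is about 14%. That is far better than raw scores, but not 5%.

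**The case against.** **Scores need not mean raw values.** Section 9.1 uses the same word, "Scores of the MSIS-29 (physical), MSWS-12 and the Disabilities of the Arm, Shoulder and Hand Score (DASH"), for a list that includes the MSWS-12 and DASH, which 13.5 then analyses as change. This stands. A reader might infer that the plan has chosen raw scores and ruled out change; no section says so. The literal wording points to scores, and what can be shown is that the quantity is not fixed.

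**The synopsis already gives change for the MSIS-29 (physical).** This also stands. For that scale the defect is a conflict to reconcile. It does not help the SF-36, which the synopsis list omits.

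**Section 13.1 has a general paired rule.** A signed-rank test within patients would remove stable differences between patients, and it could serve the fampridine v placebo question for the SF-36. It cannot compare responders with non-responders, who are different people. It therefore limits the consequence, because the quality of life objective need not rest on the 13.5 sentence alone, but it does not repair that sentence.

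**The sizes rest on assumptions.** True. Wide entry ranges show that patients vary, not that responders differ from non-responders at baseline. The 30% in 13.2 refers to a 25% improvement, not to the 20% responder rule, and dropout would reduce the 80. The 5% for change follows from assuming a perfectly stable gap. If part of the gap is visit-to-visit noise, change is open to regression to the mean. That is plausible here, because 9-HPT and JTT response is itself judged against Assessments 1 to 3.

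**Conclusion.** The point holds as an unspecified quantity in a secondary analysis, with a direct conflict between the synopsis and 13.5 for the MSIS-29 (physical) and no mention of change anywhere for the SF-36. Followed literally, the plan lets pre-treatment differences between outcome-defined groups enter the result. With 24 v 56 patients and a stable gap of 0.3 to 0.5 SD, false positives would be about 20 to 50% on raw scores and about 5% on change. The gap and the correlation are assumptions, so these figures show the mechanism and do not predict what this trial will find.

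Two stronger readings are not supported. One is that the responder groups are self-selected: they are classified from measured test results. The other is that using change would turn the comparison into an estimate of the drug's effect: it removes a stable baseline gap, but the groups remain non-randomised and the result remains an association. The primary endpoint is not affected.

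**What to change.** 1. In the last paragraph of 13.5, and in the same sentence in 9.4 and 10.3.2, replace *scores* with change in the MSIS-29 (physical) and SF-36 from the pre-treatment baseline (mean of Assessments 1 and 3) to the end of the fampridine period (Assessment 5 or 8, according to sequence). The alternative is the on-treatment score at that visit adjusted for the same baseline. Name one as the main analysis before unblinding. Change agrees with the synopsis and with endpoints c and d; adjustment is less exposed to regression to the mean but leaves part of a stable gap.
2. Add the SF-36 to the list in the synopsis statistical methods.
3. Report baseline MSIS-29 (physical) and SF-36 scores for responders and non-responders beside the result.
4. Describe the result as an association with response, not as a treatment effect.

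The cost is a few sentences of wording and one small table; all the data are already scheduled. The downside is small: change is noisier than the raw score if the correlation between visits is low (below 0.5 with a single baseline), and it can be affected by regression to the mean.

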13.0 STATISTICS

13.1 DESCRIPTION OF STATISTICAL METHODS

Outcome will be assessed using the Wilcoxon Signed Rank test to establish whether there is a difference between the paired 'on treatment' outcome measures for each individual.

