13.2 DETERMINATION OF SAMPLE SIZE SUBJECTS

Given the previous reports, one would anticipate in this observational study that approximately 30+ % of patients would experience a significant (25%) improvement in indices of upper limb and walking mobility. Using a crossover design and treating the observations as paired within individuals, and allowing for loss to follow up during the trial, a sample size of 80 (40 in each arm) will be used.

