13.7 THE LEVEL OF STATISTICAL SIGNIFICANCE

A significance level of 0.05 will be used for all analyses.

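### MSIS-29 (physical) and SF-36 are related to the timed tests only by responder status; adding a continuous association is a cheap improvement whose size depends on assumptions

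*Combined protocol and SAP*

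**What the plan says.** The last paragraph of 13.5 states that "scores on the MSIS-29 (physical) and SF-36 will be examined in relation to the objective changes (responder/non-responder) in the 9-HPT, JTT and the T25FW". Sections 9.4 and 10.3.2 repeat the sentence; in 9.4 the scores "will be examined in relation to the objective changes (responder/non-responder) in the 9-HPT, JTT and the T25FW". The synopsis adds that questionnaire change, for a list that includes MSIS-29 (physical) but not SF-36, "in responders and non-responders will be examined by the Wilcoxin Signed Rank test".

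The rules behind the label differ by test (13.5):

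- 9-HPT: both on-treatment assessments "improving 20% from the average of the baseline assessments (1, 2 & 3").
- JTT: a 20% improvement in the average on-treatment time.
- T25FW: both on-treatment walks better than the best of four off-treatment walks, as I read it.

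Section 13.2 expects that "approximately 30+ % of patients would experience a significant (25%) improvement in indices of upper limb and walking mobility" and concludes that "a sample size of 80 (40 in each arm) will be used". Section 13.7 sets the level: "A significance level of 0.05 will be used for all analyses". Section 13.1 says "Outcome will be assessed using the Wilcoxon Signed Rank test", applied to paired on-treatment measures within each patient. That is a comparison of treatments and does not link change in a timed test to change in a questionnaire.

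**The concern.** The paragraph concerns whether patient-reported impact and quality of life move with objective change in hand and walking tests. Those tests are times, recorded at all nine assessments, and the plan turns each into yes or no before relating it to the questionnaires. Under the 9-HPT rule, a patient with gains of 19% and 25% at the two visits is grouped with one who got worse, and a gain of 21% counts the same as 45%. The expected gain of 25% lies only 5 percentage points above the cut, and the cut must be met twice, so one noisy visit can move a true improver into the non-responder group.

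The prediction objectives in 9.2 are framed as response or non-response, so they need a label for MSWS-12, DASH and AMSQ. No objective needs one for MSIS-29 or SF-36. At stake is the reading of a null result: with a small responder group, it could be taken to mean that faster hands do not help patients when the comparison simply had low power.

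**Working it through.** **The plan's own figure.** The only stated figure is N=80, with no power, SD, correlation, placebo rate or dropout rate. It cannot be reproduced uniquely. For two independent groups of 40, 30% against an assumed 5% gives 85% power, and 30% against 10% gives 61%. Nothing there bears on the questionnaire analysis.

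**Inputs.**
- From the documents: n=80; 30% of patients improving 25%; three baseline and two on-treatment visits; the 20% cut; level 0.05.
- Assumed: two-sided testing; the other 70% do not change; within-patient CV of the 9-HPT from 2 to 15%; a questionnaire difference of 0.5 to 0.9 SD between improved and unimproved patients; no dropout. I used the rank-sum test for the planned contrast because responders and non-responders are independent groups.

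**Step 1: how many improvers the both-visits rule labels.** Expected improvers: 0.30 × 80 = 24. On the log scale an improver lies ln(0.80/0.75) = 0.0645 beyond the cut. One visit against the mean of three baselines has SD CV × √(1 + 1/3) = 1.155 × CV.
- CV 5%: 0.0645/0.0577 = 1.12, so one visit passes with probability about 0.87. If the two visits were independent, 24 × 0.87² ≈ 18 would be labelled.
- CV 10%: 0.0645/0.1155 = 0.56, probability about 0.71, giving 24 × 0.71² ≈ 12.

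The shared baseline makes the visits positively correlated and raises these slightly. Simulated mean numbers labelled are 18.5, 14.7, 13.4 and 12.5 at CV 5, 8, 10 and 15%. Nearly all are true improvers; even at CV 15% about 11 of the 12.5 are.

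**Step 2: power, two-class model, 9-HPT.** Simulation with 1,500 trials per cell. Each entry is rank-sum on responder status v regression on mean log change (%).

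| CV | 0.5 SD | 0.7 SD | 0.9 SD |
|---|---|---|---|
| 5% | 36 v 47 | 63 v 76 | 82 v 92 |
| 8% | 29 v 42 | 47 v 67 | 69 v 86 |
| 10% | 27 v 38 | 41 v 62 | 61 v 82 |
| 15% | 19 v 29 | 32 v 46 | 46 v 66 |

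The differences here are 10 to 21 points. A repeat run gave 8 to 20, and the Monte Carlo error of a single entry is up to √(0.25/1500) ≈ 1.3 points, so I take about 8 to 20. At CV 2% the loss is about 1 to 2 points, and at CV 2 to 3% no run exceeded 4.

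**Step 3: graded benefit.** With true log change Normal (SD 0.13) and an assumed correlation of 0.3 to 0.4 with questionnaire change, the loss is about 27 to 47 points (for example 24% v 59% at CV 10%, correlation 0.3).

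**Step 4: closed-form check.** For bivariate normal data cut so that a share p respond, the correlation shrinks by φ(z_p)/√(p(1−p)). At p=0.30 this is 0.348/0.458 = 0.759, and 0.759² = 0.576 of the efficiency is kept. Power is Φ(atanh(ρ)·√(n−3) − 1.96). At n=80:
- ρ=0.15: 26% v 17%
- ρ=0.20: 43% v 27%
- ρ=0.30: 78% v 53%
- ρ=0.40: 96% v 79%

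The loss is 9 to 25 points. With n=64 (20% dropout assumed) it is 8 to 24.

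**Step 5: the other tests and a rank-based alternative (two-class model).**
- A 20%-on-average rule, as for the JTT, loses about 0 to 5 points (CV 10%: 34 v 37, 59 v 61, 81 v 84).
- The T25FW rule loses 2 to 14 points (17 to 35 if benefit is graded).
- Rank-sum against Spearman, 9-HPT: at CV 5% the cut does better (36 v 31, 62 v 58, 84 v 79). At CV 8% the continuous analysis gains about 4 to 9 points.

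**The case against.** The strongest reply is that the loss is a product of the reviewer's assumptions. Section 13.2 supplies a response share and a size of gain, and nothing on noise, questionnaire effect or correlation. With little visit noise the loss nearly vanishes. Step 2 also changes two things at once, the cut and the move from a rank test to a parametric one, while the plan favours rank tests. Much of the two-class 9-HPT loss comes from requiring 20% at both visits, as the average rule shows. All of this stands, and it is why the size has to be given as a conditional range.

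It can also be said that the SF-36 objective in 9.2 is the effect of fampridine on quality of life, which is a treatment comparison; that one responder framework is used consistently for all the questionnaires; and that 13.10 allows documented additional analyses. These points make the matter minor. They do not remove it, because an association chosen after the data are seen carries less weight than one stated now.

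A reader might infer four stronger things that the documents do not support:

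- That the plan's own response assumption implies a fixed loss of power. It does not, for the reasons above.
- That the label discards most of the information. The normal model keeps 0.576 of it.
- That the labelled responders are misclassified. Nearly all are true improvers; the errors are improvers left out.
- That this is the only analysis covering SF-36. The paired test in 13.1 applies to outcome measures generally.

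**Conclusion.** The point holds as a cheap improvement to a secondary analysis, and it is minor. The text relates MSIS-29 (physical) and SF-36 to the timed tests only by responder status, and no continuous association is planned.

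The size ranges from almost nothing to substantial: negligible if the 9-HPT is nearly noise-free and patients split cleanly into two classes, moderate at a CV of 5 to 15%, and large if benefit is graded. The two-class figures for the 9-HPT should not be carried over to the JTT, where the loss is small, and they rest on regression being the comparator. The documents do not show which case applies. Regression on log change did not do materially worse than the cut in any scenario examined, so adding it beside the planned comparison gives nothing up.

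**What to change.** In 13.5, 9.4 and 10.3.2 keep the responder/non-responder comparison and add after it:

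*The change in MSIS-29 (physical) and SF-36 from baseline to the fampridine phase will also be regressed, separately for each test, on the log change in 9-HPT, JTT and T25FW time (mean of the two fampridine visits v baseline), with sequence as a covariate, and the slope reported with its 95% confidence interval.*

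Fitting each test separately avoids entering two hand tests that are likely to be correlated in one model. The added text should also state the questionnaire baseline, since the schedule of events records the questionnaires at assessments 1 and 3 but not at 2.

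The cost is one added sentence in three places and a little more analysis. All the data are already collected, so no visits or patients are added, and the primary endpoint is untouched. The downside is that a slope is less immediate to clinicians than two group means, which is a reason to keep the responder comparison alongside it.
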